10.5.3 Visit 3 (Day 56 ± 4 Days): Test-of-Cure/End of Study

1. **Perform Pregnancy Test:** A urine pregnancy test will be required of all female patients of childbearing potential.
2. **Record Vital Signs:** The patient's vital signs will be recorded (blood pressure, pulse, temperature and respiration rate).
3. **Review and Assessment of Concomitant Medications:** Review the patient's use of any new or ongoing concomitant medications since last visit.
4. **Review and Assessment of Adverse Events:** Patients will be questioned about any health status changes/AEs since last visit. All AEs will be recorded.
5. **Assess Local Signs and Symptoms:** Clinical signs and symptoms of tinea pedis at the target lesion site identified at Visit 1 will be evaluated using the static scale in Appendix A. Wherever possible, the same Investigator should attempt to perform all clinical exams at all visits for an individual patient.
6. **Collect Sample for KOH Wet Mount:** Patients with positive baseline culture results will have a sample for the KOH wet mount obtained from the designated target lesion site as per

CONFIDENTIAL PROTOCOL

A Randomized, Double-Blind, Vehicle-Controlled, Parallel-Design, Multiple-Site Clinical Study to Evaluate the Therapeutic Equivalence of Ketoconazole Cream 2% (Encube Ethicals Pvt Ltd) to Ketoconazole Cream 2% (G&W Laboratories Inc.) in the Treatment of Tinea Pedis

instructions in section 10.6.9. The KOH wet mount review should be performed by the Investigator or appropriately trained and qualified delegated staff.

7. **Collect Sample for Mycological Culture:** Patients with positive baseline culture results will have a sample sent to the centralized laboratory for fungal culture. Patients with a positive KOH wet mount at this visit will not have a mycological culture sample collected.
8. **Collect and Review Patient Diary:** Collect previously dispensed diary and review for compliance with the protocol.
9. **Collect Study Product:** Study product tubes that were not returned at Visit 2 will be collected.
10. Discharge from study.

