10.6.9 Collect Sample for KOH Wet Mount

If the signs and symptoms of tinea pedis meet the inclusion criteria at Visit 1, then samples for the KOH wet mount and fungal culture should be obtained from the target lesion site. After clinical assessments and before possible randomization, sufficient sample should be obtained to perform both KOH wet mount and mycological culture. The sample for the KOH wet mount should be placed onto a clean glass slide. The target lesion site should not be cleansed or sterilized before sample collection. A drop of 10% KOH should then be added to the slide and covered with a cover slip. The slide should be gently heated and then observed under the microscope. The KOH wet mount assessment will be conducted at the investigative site by the Investigator or appropriately trained and qualified delegated staff. The results of the KOH wet mount test will be entered in the patient’s source and electronic case report form (eCRF), as appropriate. Only those patients that have a positive KOH wet mount for tinea pedis (presence of

CONFIDENTIAL PROTOCOL

A Randomized, Double-Blind, Vehicle-Controlled, Parallel-Design, Multiple-Site Clinical Study to Evaluate the Therapeutic Equivalence of Ketoconazole Cream 2% (Encube Ethicals Pvt Ltd) to Ketoconazole Cream 2% (G&W Laboratories Inc.) in the Treatment of Tinea Pedis

segmented fungal hyphae under microscopic examination) at Visit 1 will have samples sent for fungal culture.

If the results of the baseline mycological culture are positive, samples for KOH will be obtained from the target lesion site at Visit 3. All efforts should be made to attempt valid skin scrapings for microscopic examinations at Visit 3, even in case of virtually healed lesions as appropriate. If the results of the baseline culture are negative, patient should be discontinued and no KOH wet mount is necessary.

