11.3.2 Modified Intent-to-Treat Population

The mITT population will include: randomized patients who:

- Met all inclusion/exclusion criteria.
- Applied at least one dose of assigned product.
- Had at least one post-baseline evaluation.
- Had a positive baseline KOH and fungal culture for *Trichophyton rubrum*, *Trichophyton mentagrophyties* or *Epidermophyton floccosum*.

Patients discontinued early for reasons other than lack of treatment effect will be excluded from the PP population and included in the mITT population using LOCF. Patients who qualify for inclusion in the mITT population with missing endpoint data who were not discontinued for lack

CONFIDENTIAL PROTOCOL

A Randomized, Double-Blind, Vehicle-Controlled, Parallel-Design, Multiple-Site Clinical Study to Evaluate the Therapeutic Equivalence of Ketoconazole Cream 2% (Encube Ethicals Pvt Ltd) to Ketoconazole Cream 2% (G&W Laboratories Inc.) in the Treatment of Tinea Pedis

of treatment effect will also be evaluated using LOCF; that is, if a patient who was not discontinued for lack of treatment effect does not have KOH or mycological culture results at Visit 3, this patient will be evaluated for the primary and secondary endpoints using LOCF from Visit 1. Patients who discontinued because of lack of treatment will not have LOCF performed.

Patients who meet the criteria above, but who also used topical drug therapy on the feet for the treatment of irritation or pruritus after the treatment phase of the study will be included in the mITT as Therapeutic Failures. If no mycological testing is performed, these patients will be considered Therapeutic Failures in the primary analysis but the Mycological Cure data will be set to missing for the secondary endpoint. No LOCF will be performed.

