6. EFFICACY VARIABLES AND EFFICACY ENDPOINTS

Efficacy Variables

The primary and secondary efficacy variables are the outcome of the KOH test (negative or positive), outcome of the mycological culture (negative or positive), and signs and symptoms scores.

Primary Efficacy Endpoint:

The primary efficacy endpoint is the proportion of patients in each treatment group with a Therapeutic Cure of tinea pedis at the test-of-cure visit two weeks after the end of treatment (Day 56 ± 4).

Secondary Efficacy Endpoints:

The secondary efficacy endpoints are:

- The proportion of patients in each treatment group with a Clinical Cure at Day 56 ± 4 .
- The proportion of patients in each treatment group with a Mycological Cure at Day 56 ± 4 .

Definitions

1. **Therapeutic Cure:** To be considered a Therapeutic Cure, the patient must have both Clinical and Mycological Cure of tinea pedis.
2. **Therapeutic Failure:** A patient will be considered a Therapeutic Failure if:

NOVUM PHARMACEUTICAL RESEARCH SERVICES
STATISTICAL ANALYSIS PLAN

Ketoconazole Cream 2%

Protocol / Study No. 71875502

- a. the patient is a Clinical or Mycological Failure
- b. the patient was considered to have an insufficient therapeutic response
- c. the patient used topical drug therapy for irritation or pruritus on the feet between Visit 2 (Day 42 ± 4 days) and Visit 3 (Day 56 ± 4 days)
3. **Clinical Cure:** To be considered a clinical cure the patient's total severity score must be ≤ 2 with no individual severity score > 1 .
4. **Clinical Failure:** A patient will be considered a Clinical Failure if the patient's total severity score is > 2 or any individual score is > 1 .
5. **Mycological Cure:** To be considered a mycological cure the patient must have a negative KOH test and a negative fungal culture.
6. **Mycological Failure:** A patient will be considered a Mycological Failure if the patient's KOH test is positive or the patient's fungal culture is positive.

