7. STUDY POPULATIONS

Per-Protocol Population

The PP population will include all randomized patients who:

- Met all inclusion and exclusion criteria.
- Made the final study visit within the protocol window of Day 56 ± 4 days (Day 52 to Day 60 inclusive) with no protocol violations that would affect the treatment evaluation.
- Did not have any significant protocol deviations.
- Were compliant with dosing between 75%-125% of the required doses.
- Had a positive baseline KOH and fungal culture for *Trichophyton rubrum*, *Trichophyton mentagrophyties* or *Epidermophyton floccosum*.

Patients discontinued from the study because of lack of treatment effect after completing at least 14 days of treatment will be included in the PP population as Therapeutic Failures provided they had a positive baseline KOH, positive baseline fungal culture, and did not have any significant protocol deviations. For these patients, there will be no mycological testing at time of discontinuation; therefore, they will be considered Therapeutic Failures in the primary analysis but the Mycological Cure data will be set to missing for the secondary endpoint.

NOVUM PHARMACEUTICAL RESEARCH SERVICES
STATISTICAL ANALYSIS PLAN

Ketoconazole Cream 2%

Protocol / Study No. 71875502

Patients who meet the criteria above, but who also used topical drug therapy for irritation or pruritus on the feet after the treatment phase of the study will be included in the PP population as Therapeutic Failures. If no mycological testing is performed, the patients will be considered Therapeutic Failures in the primary analysis but the Mycological Cure data will be set to missing for the secondary endpoint.

All analyses performed using the PP population will be done on an observed case basis (i.e., no last observation carried forward [LOCF] will be performed).

Modified Intent-to-Treat Population

The mITT population will include randomized patients who:

- Met all inclusion/exclusion criteria.
- Applied at least one dose of assigned product.
- Had a positive baseline KOH and fungal culture for *Trichophyton rubrum*, *Trichophyton mentagrophyties* or *Epidermophyton floccosum*.

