8.2 Efficacy Analyses

8.2.1 Efficacy Analyses on Primary and Secondary Endpoints

Therapeutic Equivalence

Therapeutic equivalence will be evaluated for the primary endpoint in the per-protocol (PP) population. If the 90% confidence interval (calculated using Yates' continuity correction) on the absolute difference between the proportion of patients with a Therapeutic Cure in the Test and Reference groups ($p_T - p_R$) is contained within the range [-20%, +20%] then therapeutic equivalence of the Test product to the Reference product will be considered to have been demonstrated.

The same statistical approach will be conducted for analyses of the secondary endpoints in the PP population.

To declare therapeutic equivalence of the Test product to the Reference product, equivalence must be demonstrated for only the primary endpoint in the PP population.

Patients who are missing mycological culture data at the test-of-cure visit will not be included in the analysis for the secondary endpoint of Mycological Cure.

Superiority to Placebo

NOVUM PHARMACEUTICAL RESEARCH SERVICES
STATISTICAL ANALYSIS PLAN

Ketoconazole Cream 2%

Protocol / Study No. 71875502

Superiority of the Test and Reference products against the Placebo product for the primary endpoint will be evaluated in the mITT population using, if necessary, LOCF as described in section 11.3.2 of the protocol.

Patients discontinued early for reasons other than lack of treatment effect will be excluded from the PP population and included in the mITT population using LOCF. Patients who qualify for inclusion in the mITT population with missing endpoint data who were not discontinued for lack of treatment effect will also be evaluated using LOCF; that is, if a patient who was not discontinued for lack of treatment effect does not have KOH or mycological culture results at Visit 3, this patient will be evaluated for the primary and secondary endpoints using LOCF from Visit 1. Patients who discontinued because of lack of treatment will not have LOCF performed.

Patients who meet the criteria above, but who also used topical drug therapy on the feet for the treatment of irritation or pruritus after the treatment phase of the study will be included in the mITT as Therapeutic Failures. If no mycological testing is performed, these patients will be considered Therapeutic Failures in the primary analysis but the Mycological Cure data will be set to missing for the secondary endpoint. No LOCF will be performed.

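### Read literally, the mITT carry-forward rule for missing Visit 3 mycology also resets Clinical Cure to Visit 1 scores, which always gives Clinical Failure (secondary endpoint only)

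*SAP*

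**What the plan says.** The rule stands in four places with the same content: Protocol 11.3.2 and SAP 7, 8.2.1 and 8.5. It concerns an mITT patient who was not discontinued for lack of effect and who lacks KOH or culture results at Visit 3. SAP 8.2.1 says "this patient will be evaluated for the primary and secondary endpoints using LOCF from Visit 1"; Protocol 11.3.2 says the patient "will be evaluated for the primary and secondary endpoints using LOCF from Visit 1". Two groups get no LOCF: patients discontinued for lack of effect, and patients who used topical therapy for irritation or pruritus after the treatment phase.

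SAP 6 lists two secondary endpoints, Clinical Cure and Mycological Cure. For Clinical Cure the "total severity score must be ≤ 2 with no individual severity score > 1". Neither KOH nor culture enters that definition. Protocol 10.5.3 item 5 schedules the scores at Visit 3 without reference to mycology: "Clinical signs and symptoms of tinea pedis at the target lesion site identified at Visit 1 will be evaluated using the static scale". Scores are also rated at Visit 2 (Protocol 10.5.2), whereas KOH and culture are scheduled only at Visits 1 and 3.

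For the per-protocol (PP) population, SAP 7 states: "All analyses performed using the PP population will be done on an observed case basis". Shell T14.2.10 shows Clinical Cure for both populations, and its footnote applies LOCF to the mITT superiority test.

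**The concern.** The trigger is a missing mycology result, but the stated consequence reaches every endpoint, and no sentence preserves observed severity scores. For KOH and culture, Visit 1 is the only earlier observation, so carrying it forward is at least coherent. For severity it is not the last observation: Visit 2 and Visit 3 scores may both exist, and going back to Visit 1 is baseline carried forward over observed data.

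A patient with healed Visit 3 scores and no mycology would then be a Clinical Failure in the mITT half of T14.2.10. If that patient also qualifies for PP, the same scores make the patient a Clinical Cure in the PP half. Two programmers working from this SAP could also derive different mITT Clinical Cure values. At stake is the mITT superiority comparison on one secondary endpoint.

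**Working it through.** **1. The plan's own power figure.** The nearest stated figure is at least 99% power for superiority on Therapeutic Cure (Protocol 11.2, SAP 5): 216 vs 108 patients, 40% vs 10%, two-sided 5%, pooled Z-test with continuity correction.
- Pooled rate = (216×0.40 + 108×0.10)/324 = 0.30
- SE0 = √[0.30×0.70×(1/216 + 1/108)] = 0.0540
- SE1 = √[0.40×0.60/216 + 0.10×0.90/108] = 0.0441
- Correction = 0.5×(1/216 + 1/108) = 0.0069
- z = (0.30 − 0.0069 − 1.96×0.0540)/0.0441 = 4.25, so power is about 99.999%.

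The stated figure reproduces. The plan gives no power for Clinical Cure.

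**2. What Visit 1 scores give.** Every mITT patient met the entry criteria (SAP 7). Protocol 10.3.1 item 7 requires erythema ≥ 2, and pruritus or scaling ≥ 2. Each of the six items is scored 0-3, so there are 4⁶ = 4,096 patterns. Those meeting entry number 2 (erythema) × 12 (pruritus/scaling pairs with at least one ≥ 2) × 64 (other three items) = 1,536; the total ≥ 4 follows automatically. None is a Clinical Cure, since erythema alone exceeds 1. Carrying Visit 1 scores forward gives Clinical Failure in every case.

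**3. Which endpoints change.** Cross Visit 3 clinical status (cure, fail) with KOH (negative, positive, missing) and culture (negative, positive, missing): 18 cells. Compare the literal rule with carry-forward of the missing mycology only. Five cells differ, all with observed clinical cure and KOH or culture absent. In each, only Clinical Cure changes. Mycological Cure and Therapeutic Cure are identical in all 18 cells, because mITT membership requires positive baseline KOH and culture, and carrying either forward already means failure. One of the five cells is KOH positive with no culture, which is discussed under the objection.

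**4. Size, on assumptions.** Let m be the share of an arm with Visit 3 scores but no mycology, and CC its Clinical Cure rate. The documents give neither. Assume m = 2-10%, CC = 50-70% on Test and 20-40% on Placebo, and affected patients cured at their arm's rate.
- Loss = m×CC. Test: 0.02×50 = 1.0 to 0.10×70 = 7.0 points (2.2 to 15.1 of 216 patients). Placebo: 0.02×20 = 0.4 to 0.10×40 = 4.0 points (0.4 to 4.3 of 108).
- Change in the Test−Placebo gap = −m_T×CC_T + m_P×CC_P. Equal m: −0.02×(50−40) = −0.2 to −0.10×(70−20) = −5.0. Unequal m: −0.10×70 + 0.02×20 = −6.6 to −0.02×50 + 0.10×40 = +3.0.
- If every affected patient is healed (upper bound), the loss is m itself, 2 to 10 points per arm, and the gap changes by m_P − m_T, from −8 to +8.

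**5. Power of the secondary test, on the same assumptions.** Pooled Z-test, 216 vs 108, no continuity correction, as an unstratified stand-in for the CMH test. Derived rate = CC×(1−m).

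| True CC, Test/Placebo (%) | m, Test/Placebo (%) | Derived rates (%) | Gap (points) | Power (%) |
|---|---|---|---|---|
| 60/40 | 0/0 | 60.0/40.0 | 20.0 | 92.9 |
| 60/40 | 10/10 | 54.0/36.0 | 18.0 | 87.0 |
| 60/40 | 10/2 | 54.0/39.2 | 14.8 | 71.3 |
| 60/40 | 2/10 | 58.8/36.0 | 22.8 | 97.6 |
| 60/30 | 10/2 | 54.0/29.4 | 24.6 | 99.1 (from 99.96) |
| 70/40 | 10/2 | 63.0/39.2 | 23.8 | 98.4 (from 99.95) |
| 50/20 | 10/2 | 45.0/19.6 | 25.4 | 99.7 (from 99.99) |

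With continuity correction the four 60/40 rows become 91.1, 84.3, 67.1 and 96.8.

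**The case against.** The strongest reply is that no sentence says observed Visit 3 scores are replaced. LOCF means carrying the last observation forward, it is to be used if necessary, and the rule opens by addressing patients whose endpoint data are missing. An observed Visit 3 score is neither missing nor superseded. Visit 1 is named because it is the only earlier visit with mycology. This stands as a reasonable account of intent: the override follows from the literal wording and is not stated outright. It does not remove the defect, because the sentence names the secondary endpoints without limit. The paragraph after it, on topical-therapy users, shows that the authors could write a rule for mycology alone when they meant one.

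It is also fair that the documents do not show such patients will occur. Sites must "attempt valid skin scrapings for microscopic examinations at Visit 3, even in case of virtually healed lesions", which works to reduce missing samples. The rule "Patients who are missing mycological culture data at the test-of-cure visit will not be included in the analysis" shows that missing cultures were foreseen, but it concerns Mycological Cure and sits under PP equivalence. That Clinical Cure is understated in every arm, or that the best-healed patients are the ones failed, is therefore conditional. So is the conflict between the two halves of T14.2.10, which needs a patient without mycology to remain in PP.

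The power loss depends on the chosen scenario. It is material at an assumed 20-point gap, most of all with unequal missingness, for which no passage gives support in a double-blind trial. The only active-placebo gap the plan states is at least 30 points (40% vs 10%), and that is for Therapeutic Cure.

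A reader might infer that completers with a positive Visit 3 KOH, whose culture is omitted by design, are also caught by the rule. SAP 6 settles this: "A patient will be considered a Mycological Failure if the patient's KOH test is positive". Their mycology is observed, not missing.

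**Conclusion.** The concern holds as a derivation rule that is wrong as written for one secondary endpoint. Taken literally, an mITT patient with healed Visit 3 scores and no Visit 3 mycology counts as a Clinical Failure, with certainty, unless one of the two no-LOCF exceptions applies. Any such patients lower the mITT Clinical Cure rate in their arm, and the active-placebo difference can move either way.

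The size cannot be fixed from the documents; the ranges above rest on assumed missingness and cure rates. In the three 30-point scenarios, with affected patients cured at their arm's rate, power stays above 98% (uncorrected Z-test) even with 10% missing on Test and 2% on Placebo.

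A reader might go further and infer that the superiority claim is biased. The documents do not support that. Therapeutic Cure is the same under either reading, SAP 8.2.1 declares superiority on the primary endpoint alone, and PP equivalence uses observed cases. The scores themselves also remain visible in T14.2.7.1 and L16.2.6.1. The point should be fixed, but it does not threaten the main conclusions.

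**What to change.** Amend SAP 7, 8.2.1 and 8.5, and list the departure from Protocol 11.3.2 in SAP 8.7:

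1. Apply the Visit 1 carry-forward only to the KOH or culture component that is missing.
2. Derive mITT Clinical Cure from the severity scores observed at the scheduled test-of-cure assessment (Day 56 ± 4), whatever the mycology status.
3. State the rule for patients with no test-of-cure score: either the last available score is carried forward or the patient counts as a failure. Report the number per arm. Early terminators belong here. Protocol 12.2.4 has the Visit 3 form completed for them and the shells merge Visit 3 with early termination, but those scores are not Day 56 observations.
4. Keep both no-LOCF exceptions. A note that a positive Visit 3 KOH is an observed Mycological Failure is optional, since SAP 6 already says so.

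The cost is wording and derivation code, with no new data. mITT Clinical Cure rates and the active-placebo difference may change slightly, in either direction. Under item 3, carrying an earlier score forward ignores relapse after treatment ends, while counting failure understates cure. The change should be made before database lock, when Protocol 11.1 requires the SAP to be final, so that it cannot look driven by results.

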8.3 Safety Analysis

8.3.1 Adverse Events

All the adverse events (AEs) reported throughout the study will be coded and classified according to the MedDRA (Medical Dictionary for Regulatory Activities) coding dictionary (Version 21.0 or higher).

Treatment emergent adverse events (TEAE) are those that have a start date after the study treatment has been administered or the events that were present before administration of study treatment and worsen in severity after administration of study treatment. Treatment emergent adverse events will be summarized and analyzed in a summary table. Pre-treatment adverse events will be presented in the listing.

A summary table of the number and percent of patients with TEAEs by system organ class, preferred term, and treatment will be presented. Each patient will be counted only once within each preferred term.

A frequency summary table of the number of TEAEs by system organ class, preferred term, severity, and treatment will be presented. Severity will be classified as “Mild”, “Moderate”, or “Severe”.

Similarly, a frequency summary table of the number of TEAEs by system organ class, preferred term, and relationship to a study drug, and treatment will be presented. Relationship to a study drug will be classified as “Not Related” or “Related”.

If sufficient data exist, then TEAE frequencies will be compared among the three treatments using Fisher’s exact test; if this test is statistically significant at the 5% significance level, then a pairwise Fisher’s exact test comparing Test and Reference will be conducted.

TEAEs will be listed by treatment group and patient. Pre-treatment adverse events will be listed by patient.

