2. OBJECTIVES

1. Evaluate the therapeutic equivalence of a generic Ketoconazole Cream 2% (Encube Ethicals Pvt Ltd) to the Reference product, Ketoconazole Cream 2% (G&W Laboratories Inc.) in the treatment of tinea pedis.
2. Demonstrate the superiority of the clinical effect of the Test and Reference (active) products over that of the Placebo (vehicle) in the treatment of tinea pedis.
3. Compare the safety of the Test, Reference and Placebo products in the treatment of tinea pedis.

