To allow for approximately 35% of patients who may have negative fungal cultures post-randomization, drop out from the study or are otherwise non-evaluable, approximately 830 patients may be randomized (332 in each active group and 166 in the Placebo group) to yield 540 patients in the mITT population.

More than 50% of the patients should have baseline fungal cultures that test positive for *T. rubrum*. If fewer than 50% of enrolled patients have a positive *T. rubrum* culture or the number of patients with negative fungal cultures is more than anticipated, then additional patients may be enrolled to ensure that at least 430 (172:172:86) patients are eligible in the PP population, of which > 50% have a positive *T. rubrum* culture at baseline.

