8. STATISTICAL ANALYSIS METHODS

If not otherwise specified, statistical significance is defined as $p < 0.05$ and is two-tailed. Data will be summarized with respect to demographic and baseline characteristics and safety

NOVUM PHARMACEUTICAL RESEARCH SERVICES
STATISTICAL ANALYSIS PLAN

Ketoconazole Cream 2%

Protocol / Study No. 71875502

variables.

For categorical variables, the number and percent of each category within a parameter will be calculated. For continuous variables, statistics will include n, mean, standard deviation, median and range.

All statistical analyses will be conducted using SAS®, Version 9.4 or higher. Datasets will be prepared using headings from Clinical Data Interchange Consortium (CDISC) Study Data Tabulation Model (SDTM) implementation for human clinical trials and ADaM (Analysis Dataset Model) and FDA Guidance of Technical Specifications - Comparative Clinical Endpoints Bioequivalence Study Analysis Datasets for Abbreviated New Drug Application (September 2018) .

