8.4 Multiple Comparisons

No multiple comparison adjustment will be made in this study.

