Patients with at least one AE	xxx (xx.x)	xxx (xx.x)	xxx (xx.x)	xxx (xx.x)
Discontinued study product due to above AE	xxx (xx.x)	xxx (xx.x)	xxx (xx.x)	xxx (xx.x)
AEs reported	Xxx	xxx	xxx	xxx
Mild	xxx (xx.x)	xxx (xx.x)	xxx (xx.x)	xxx (xx.x)
Moderate	xxx (xx.x)	xxx (xx.x)	xxx (xx.x)	xxx (xx.x)
Severe	xxx (xx.x)	xxx (xx.x)	xxx (xx.x)	xxx (xx.x)
Not Related	xxx (xx.x)	xxx (xx.x)	xxx (xx.x)	xxx (xx.x)
Related	xxx (xx.x)	xxx (xx.x)	xxx (xx.x)	xxx (xx.x)
Death	xxx (xx.x)	xxx (xx.x)	xxx (xx.x)	xxx (xx.x)
Serious AE	xxx (xx.x)	xxx (xx.x)	xxx (xx.x)	xxx (xx.x)

Test: Ketoconazole Cream 2% (Encube Ethicals Pvt Ltd)

Reference: Ketoconazole Cream 2% (G&W Laboratories Inc.; Registrant: Teva Pharmaceuticals USA Inc.)

Placebo: Placebo Cream (Test vehicle) (Encube Ethicals Pvt Ltd)

MedDRA Version 21.0

PROGRAM: L:\DEV\755\71875502\SAS\PGM\XXXX

Created on: ddmmmyy hh:mm

OUTPUT: L:\DEV\755\71875502\SAS\OUT\XXXX

Page 1 of N

NOVUM PHARMACEUTICAL RESEARCH SERVICES
STATISTICAL ANALYSIS PLAN

Ketoconazole Cream 2%

Protocol / Study No. 71875502

T14.3.2 Summary of Frequency of Adverse Events by Body System
(Safety Population)

Body System	Preferred Term	Test N = xxx		Reference N = xxx		Placebo N = xxx		Overall Fisher's P-value	Fisher's P-value Test vs. Reference
		Events	Patients n (%)	Events	Patients n (%)	Events	Patients n (%)		
Patients with at least one AE	Total	xx	xxx (xx.x)	xx	xxx (xx.x)	xx	xxx (xx.x)	0.1234	NA
Ear and labyrinth disorders etc.	Ear pain	xx	xxx (xx.x)	xx	xxx (xx.x)	xx	xxx (xx.x)	0.0425	0.0372

etc.

Test: Ketoconazole Cream 2% (Encube Ethicals Pvt Ltd)

Reference: Ketoconazole Cream 2% (G&W Laboratories Inc.; Registrant: Teva Pharmaceuticals USA Inc.)

Placebo: Placebo Cream (Test vehicle) (Encube Ethicals Pvt Ltd)

N = number of patients in safety population in that particular group; n= number of patients with data available for that particular group; total % is based on N

MedDRA Version 21.0

Note to programmer: If the global Fisher's exact test is statistically significant among the three treatment groups at the 5% alpha level (i.e. p < 0.05), then Fisher's exact test using only the test and reference groups will be performed to identify any potential statistically significant differences that are clinically relevant between the two active treatment groups.

PROGRAM: L:\DEV\755\71875502\SAS\PGM\XXXX
 Created on: ddmmmyy hh:mm

OUTPUT: L:\DEV\755\71875502\SAS\OUT\XXXX
 Page 1 of N

NOVUM PHARMACEUTICAL RESEARCH SERVICES
STATISTICAL ANALYSIS PLAN

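### Test and Reference adverse events are tested against each other only after a significant three-arm Fisher test, and no Test–Reference difference or interval is planned, so a borderline Test excess can go formally untested

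*SAP*

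**What the plan says.** The third objective is to "Compare the safety of the Test, Reference and Placebo products in the treatment of tinea pedis" (SAP 2).

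For this, SAP 8.3.1 states that, where data are sufficient, "TEAE frequencies will be compared among the three treatments using" Fisher's exact test. The next step is conditional: "if this test is statistically significant at the 5% significance level, then a pairwise" Fisher test of Test against Reference is done. Protocol 11.8 has the same two-step rule.

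The programmer's note under shell T14.3.2 (SAP 9) repeats it. After a significant global test, Fisher's "exact test using only the test and reference groups will be performed to identify any potential statistically significant differences". In the shell, the row for patients with at least one AE carries an overall p of 0.1234 and shows NA in the Test vs Reference column. So the overall summary row is gated as well as the preferred terms.

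Neither SAP 8.3.1 nor any T14.3 shell provides a Test–Reference difference or a confidence interval. Events and patients, n (%), are shown for each arm whatever the test result. SAP 8 sets significance at p < 0.05 "and is two-tailed", and SAP 8.4 says "No multiple comparison adjustment will be made in this study".

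**The concern.** The trial compares a generic with its reference product, so Test against Reference is a natural safety contrast to report. Under the plan, its only formal comparison depends on a test that also involves Placebo, which is the Test vehicle. A three-arm test looks for any departure from equality among three rates. When Placebo falls between the two active arms, it adds little evidence of departure but still takes up a degree of freedom. This makes the gate harder to pass than the direct comparison.

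What is at stake is modest. A Test excess that would reach p < 0.05 pairwise may be reported as NA, with no interval to show how large a difference remains compatible with the data. The interval is absent even when the gate opens, because the plan never produces one.

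**Working it through.** **Inputs.** Group sizes are "332 in each active group and 166 in the Placebo group" (SAP 5). I take the Safety population to be all randomized patients. Tests are two-sided at 0.05. The documents give no adverse event rates, so the rates below are assumptions shown over a range.

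**The plan's own figures.** 830 × 2/5 = 332 and 830 × 1/5 = 166. 830 × (1 − 0.35) = 539.5, against the 540 stated for the mITT population. The group sizes are consistent.

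**Formulas.** With a, b, c patients with an event and m = a + b + c:
- Three-arm table probability: C(332,a)·C(332,b)·C(166,c) / C(830,m). The p-value sums this over all tables with the same margins that are no more probable than the one observed.
- Pairwise: the same with C(332,a)·C(332,b) / C(664,a+b).

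**Exact p-values**

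| Test / Ref / Placebo | Pairwise p | Three-arm p | Pair tested? |
|---|---|---|---|
| 20 / 8 / 7 (6.0 / 2.4 / 4.2%) | 0.032 | 0.066 | No |
| 21 / 8 / 7 | 0.021 | 0.0425 | Yes |
| 15 / 5 / 5 (4.5 / 1.5 / 3.0%) | 0.038 | 0.071 | No |
| 16 / 5 / 5 | 0.024 | 0.046 | Yes |
| 33 / 17 / 12 (9.9 / 5.1 / 7.2%) | 0.0265 | 0.065 | No |
| 34 / 17 / 13 | 0.019 | 0.044 | Yes |
| 91 / 66 / 39 (27.4 / 19.9 / 23.5%) | 0.028 | 0.073 | No |
| 22 / 10 / 5 (Placebo equal to Reference) | 0.045 | 0.0635 | No |
| 30 / 8 / 12 (Placebo between) | 0.0003 | 0.0006 | Yes |
| 6 / 0 / 2 (rare event) | 0.0305 | 0.031 | Yes |

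The blocked band is roughly pairwise p from 0.02 to 0.05. One or two more patients with an event are enough to leave it.

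**What an interval would add (20/8/7).** Difference = 6.02% − 2.41% = 3.61 points. SE = √(0.0602 × 0.9398/332 + 0.0241 × 0.9759/332) = 1.55 points. Wald 95% CI = 3.61 ± 1.96 × 1.55, or about 0.6 to 6.7 points. The plan would print NA.

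**Chance of a significant Test excess over Reference** (simulation, 6,000 runs per scenario; 4,000 for 10/4/7%)

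| Assumed rates T/R/P | Direct | Gated | Loss (points) |
|---|---|---|---|
| 10 / 5 / 7.5% | 64.1% | 56.0% | 8.1 |
| 20 / 12 / 16% | 77.5% | 70.0% | 7.5 |
| 6 / 2 / 4% | 70.5% | 63.4% | 7.1 |
| 10 / 4 / 7% | 84% | 78% | 6 |
| 6 / 2 / 2% | 71.6% | 67.1% | 4.5 |
| 6 / 2 / 6% | 70.8% | 66.8% | 4.0 |
| 10 / 5 / 2% | 63.7% | 63.5% | 0.2 |
| 15 / 5 / 10% | 98.8% | 98.3% | 0.5 |

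**What the gate buys.** With all three true rates at 5%, a chance finding of Test above Reference falls from about 1.6% to 1.0% per term.

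**The case against.** The strongest defence is that testing all arms first and the pair second is a recognised convention, stated consistently in the protocol, the SAP text and the shell, and used for baseline characteristics in T14.2.2 too. It fits an objective that names all three products. T14.3.2 tests every preferred term, and the gate trims chance findings. The safety tests support no claim or decision rule, and the study is not sized on adverse events. This stands, and it is why removing the gate for every preferred term would be a trade-off rather than a plain gain. Intervals on many rare terms would also be hard to interpret.

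A reader might infer four stronger things that the documents do not support:
- *That the pair is never tested when Placebo lies in between.* Larger excesses pass, as 30/8/12 shows, and the blocked examples sit at the edge.
- *That a Test excess is left with no estimate.* SAP 8.3.1 commits without condition to numbers and percentages by arm, and T14.3.2 prints them. The difference can be read off two columns; what is missing is the printed difference, its interval and, below the gate, a p-value.
- *That the third objective goes unanswered.* It is answered by these tables and the three-arm test, though without an interval.
- *That the gate contradicts SAP 8.4.* That section rules out an adjustment for multiple comparisons. The sequence adjusts no p-value or significance level, and no analyst is left with two instructions.

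The defence does not explain why the summary rows should lack a Test–Reference interval.

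**Conclusion.** The point holds in a limited form. A borderline Test excess can go formally untested, mostly when Placebo lies between or equals an active arm, and no Test–Reference interval is produced in any case. With a moderate true excess, the loss of detection is about 6 to 8 points with Placebo near midway and about 4 to 5 points with Placebo equal to an active arm. It is 1 point or less for 15/5/10%. These sizes rest on assumed event rates and on a Safety population of 332/332/166.

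The primary equivalence and superiority conclusions are untouched. This is a cheap improvement and optional in severity.

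**What to change.** In SAP 8.3.1 and the T14.3.2 note, add that three summary rows will show the Test–Reference difference in the proportion of patients with an event, its 95% confidence interval and the pairwise Fisher p, regardless of the three-arm p. The rows are any TEAE, related TEAEs and treatment-area TEAEs. Label the p-values descriptive and name the interval method. The three-arm test and the gate may stay for individual preferred terms. Record the change in SAP 8.7, since Protocol 11.8 carries the same rule, and make it before unblinding.

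Cost: a sentence, a revised note, one column pair and two extra rows. No new data are needed, because listing L16.2.7.1 already holds relationship and treatment area. The downside is a few more chance p-values below 0.05, confined to three labelled rows.
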